18.3 Final Clinical Study Report

A final report will be completed, even if the study is prematurely terminated.

18.4 Publication Policy

Information concerning the study device, patent applications, processes, unpublished scientific data, the Protocol, and other pertinent information is confidential and remains the property of the Sponsor.

At the conclusion of the trial, the results may be prepared and used in support of an FDA submission and provided at a major meeting(s). The publication of results from any center experience within the trial is not allowed unless there is written consent from the Sponsor.

A publication strategy plan will be developed as a collaboration between the Principal Investigators and the Sponsor, Caerus Corporation.

20.0 APPENDICES

APPENDIX A. OrthoCor Active System - INSTRUCTIONS FOR USE (IFU)

APPENDIX B. ADVERSE EVENTS

APPENDIX A.**OrthoCor Active System - INSTRUCTIONS FOR USE (IFU)**

APPENDIX B.**Adverse Events**

The following adverse events are unexpected but may occur with use of OrthoCor Active System:

- Patient injury during use such as skin irritation or burns.

1. DOCUMENT INFORMATION

Document Details	Information
Study Number	OCM-OAS-01
Version Date and Number	23-Sep-2022 Version 2.0
Document Owner	[name]
Effective Date	23-Sep-2022

2. DOCUMENT HISTORY

Version	Effective Date	Changes	Reason for Changes	Author
1.0	23-Mar-2022	Original	N/A	[name]
2.0	23-Sep-2022	Administrative / formatting changes made throughout various sections to better align with protocol. No statistical analysis measurement details / information changed from v1.0.	Review SAP with amendment 2 to protocol OCM-OAS-01 v3.0	[name]
3.0	27-Nov-2023	Correction of typo in the PP Population definition	Error in treatment duration	[name]

3. INTRODUCTION

The purpose of this Statistical Analysis Plan (SAP) is to describe the operational aspects of statistical analysis of the efficacy and safety data to ensure endpoint analysis for primary, secondary endpoints and safety.

The objective of this study is to evaluate the OrthoCor Active System in individuals prescribed its use in comparison with Standard of Care (SOC) intervention. Pain assessments will be conducted utilizing the Mankoski Pain Scale.

4. STUDY DESIGN

This is a prospective, multi-center, randomized, open label study that will enroll up to 100 subjects. Subjects will consist of both males and females, presenting to the designated study sites with pain in superficial soft tissue, such as in the ankle, back, knee, wrist, elbow, shoulder, foot, or neck who are prescribed the use of the OrthoCor Active System or Standard of Care (SOC) intervention.

Patients will be enrolled consecutively at each participant site until up to 50 using the OrthoCor Active System and up to 50 using the Standard of Care (SOC) intervention have enrolled. The CRO will stratify the arms (OrthoCor Active System vs SOC) by selecting the arm alternatively. The patients will be enrolled consecutively at the participant site until enrollment is met.

As part of exploratory research extension, patients using the OrthoCor Active system will have the opportunity to continue the trial for an additional 2 weeks. Participants assigned SOC will have the opportunity to cross-over using the OrthoCor Active system for the additional 2 weeks. Participation in the exploratory extension is optional.

5. STUDY OBJECTIVES AND ENDPOINTS

The primary safety and efficacy objectives are:

Safety endpoint of this study will be the adverse events reported with the OrthoCor Active System after 2 weeks of use.

Efficacy endpoint of this study will be the comparison of the OrthoCor Active System pain assessment scores to the Standard of Care (SOC) intervention after 2 weeks of use. The primary effectiveness endpoint of this study is the change from baseline of the OrthoCor Active System compared to the SOC intervention.

The exploratory objectives, for publication only, are comparison of the performance of the OrthoCor Active System to standard of care after additional 2 weeks of use.

6. SUBJECT POPULATION

The target population is both female and male, over the age of 18 years pain in the superficial tissue at sites such as ankle, back, knee, wrist, elbow, shoulder, foot, or neck who meet inclusion criteria and do

not meet any exclusion criteria from the protocol. The participants will be selected from the population selected by the Principal Investigator at each of the 5 participant US sites after passing the screening and eligibility assessments per protocol.

As part of exploratory research extension, patients using the OrthoCor Active system will have the opportunity to continue the trial for an additional 2 weeks. Participants assigned SOC have the opportunity to cross-over using the OrthoCor Active system for the additional 2 weeks. Participation in the exploratory extension is optional.

7. SAMPLE SIZE

The sample size estimates are calculated assuming a binomially distributed response of improvement or no improvement. Without any a priori estimates, the most conservative estimate (widest interval) is using a baseline for the standard of care (SOC) of 50% improvement. The null hypothesis for a non-inferiority study is that the experimental treatment is inferior to the standard of care. The alternative hypothesis is that the experimental treatment is non-inferior to the standard of care.

The sample size per group is based on the comparison of two proportions with baseline proportion of 50% for the experimental treatment assuming a 50% response for SOC and a non-inferiority margin of 10% assuming 90% power. The assumed confidence is 95% or a type 1 error rate of 5%.

The study will enroll 100 subjects, up to 50 using the OrthoCor Active System and up to 50 using the Standard of Care (SOC) intervention. The patients will be enrolled consecutively at the participant site until enrollment is met. The CRO will stratify the arms (OrthoCor Active System vs SOC) by selecting the arm alternatively.

For the exploratory assessments, the 50 subjects who received SOC will have the opportunity to cross-over and use the OrthoCor Active system.

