11. GENERAL CONSIDERATIONS

11.1. General Methods

A repeated measures ANOVA will be utilized to assess statistical differences between the active and sham devices. A test of normality will be performed. If the data is not shown to be normally distributed, nonparametric methods may be used. All hypotheses are performed at an alpha equal to 0.05.

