12. STATISTICAL ANALYSIS

The data consists of multiple repeated measures and will be checked for normalcy and sphericity, and primary analysis will consist of ANOVAs for repeated measures and with other secondary analysis as appropriate for secondary hypotheses. Nonparametric methods will be used if the data is not normally distributed.

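### The SAP's only stated hypothesis is non-inferiority on a binary response, but the planned primary analysis tests for a difference in Mankoski change, so the hypothesis gets no verdict and the 90% power belongs to a test that is not planned

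*SAP*

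**What the plan says.** **Hypothesis and sizing (SAP 7).** The sample size is derived "assuming a binomially distributed response of improvement or no improvement", with 50% response in both arms and "a non-inferiority margin of 10% assuming 90% power". Type 1 error is 5%, sidedness not given. The null is that the device is inferior to standard of care (SOC). The alternative reads: "The alternative hypothesis is that the experimental treatment is non-inferior to the standard of care". Enrolment is 100, up to 50 per arm.

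**Endpoint (SAP 5 and 12.1; Protocol 11.0).** "The primary effectiveness endpoint of this study is the change from baseline of the OrthoCor Active System compared to the SOC intervention". SAP 12.1 places this on the Mankoski scale after 2 weeks of treatment.

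**Analysis (SAP 11.1 and 12).** Section 11.1 says: "A repeated measures ANOVA will be utilized to assess statistical differences between the active and sham devices". Section 12 says that "primary analysis will consist of ANOVAs for repeated measures". If the data are not normal, section 11.1 says "nonparametric methods may be used", whereas section 12 makes the switch definite. Neither section names the nonparametric method or a normality criterion.

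**Populations and missing data (SAP 11.2 and 12.4).** Efficacy is analysed on both ITT and PP, with neither named as primary. Section 12.4 plans complete cases and adds that carrying the last visit forward will be considered.

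**The concern.** A non-inferiority claim needs an estimate, a margin on the same scale, and a rule comparing a confidence limit with that margin. Section 7 supplies a margin on a difference in proportions. The analysis sections supply a difference test on a score. The two do not meet:

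- A non-significant ANOVA is not evidence of non-inferiority.
- A significant ANOVA concerns mean scores and says nothing about 10 points on a proportion.
- The 90% power describes a comparison of proportions that is not planned, so the planned test has no stated power.

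The SAP also does not say which ANOVA term decides: group, group by time, or a contrast at the end of the 2 weeks. In an open-label trial, a framework and deciding term left unsettled invite dispute over what the primary result was.

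**Working it through.** **1. The passages side by side**

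| Element | SAP 7 | SAP 5, 11.1, 12, 12.1 |
|---|---|---|
| Response | Binary, no threshold defined | Change in Mankoski score |
| Question | Non-inferior within 10% | Is there a difference |
| Method | Two proportions | Repeated-measures ANOVA |
| Decision rule | None given | Alpha 0.05, no margin |

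Non-inferiority and its margin appear only in SAP 7. Protocol section 11 names no test, and SAP 13 records no change that closes the gap.

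**2. The plan's own figure.** Inputs from SAP 7: 0.50 and 0.50, margin 0.10, 90% power. The 10% is read as absolute points (assumption). Both one-sided levels are shown because sidedness is not stated.

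n per arm = (z(1−α) + z(0.90))² × (0.25 + 0.25) / 0.10²

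- One-sided 0.05: (1.645 + 1.282)² × 0.5 / 0.01 = 428.2, so 429.
- One-sided 0.025: (1.960 + 1.282)² × 0.5 / 0.01 = 525.4, so 526.

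The planned 50 per arm is not reproduced.

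**3. Power if the stated hypothesis were tested.** SE = √(0.5/n); power = Φ(0.10/SE − z(1−α)).

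| Evaluable per arm | SE | One-sided 0.025 | One-sided 0.05 |
|---|---|---|---|
| 50 | 0.1000 | Φ(1.000 − 1.960) = 16.9% | Φ(1.000 − 1.645) = 26.0% |
| 45 (assumed) | 0.1054 | Φ(0.949 − 1.960) = 15.6% | Φ(0.949 − 1.645) = 24.3% |
| 40 (assumed) | 0.1118 | Φ(0.894 − 1.960) = 14.3% | Φ(0.894 − 1.645) = 22.7% |

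An exact binomial calculation for the Wald limit at 50 per arm gives 18.4% and 24.3%. If 10% were relative (5 points), power at 50 per arm falls to 7.2% and 12.6%. With both observed rates at 50%, the lower limit at 50 per arm is −1.960 × 0.10 = −19.6 points, or −1.645 × 0.10 = −16.4 points. Both miss −10.

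**4. What the enrolment supports on the score.** The documents give no SD, so results are in SD units of the change. Unadjusted two-sample t-test, two-sided 5%, noncentral t with noncentrality d√(n/2) and 2n − 2 degrees of freedom:

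| Evaluable per arm | 90% power | 80% power |
|---|---|---|
| 50 | 0.65 SD | 0.57 SD |
| 45 (assumed) | 0.69 SD | 0.60 SD |
| 40 (assumed) | 0.73 SD | 0.63 SD |

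For non-inferiority on the mean with no true difference, 50 evaluable per arm reaches 90% power only with a margin of about 0.65 SD (one-sided 0.025) or 0.59 SD (one-sided 0.05). The 45 and 40 rows are illustrations: SAP 7 enrols up to 50 per arm with no allowance for losses, and both documents plan complete cases.

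**The case against.** The best defence is that section 7 only sizes the trial and the real framework is a difference test. The documents do lean that way. SAP 11.1 looks for differences, Protocol 9.4 ties early completion to a significant improvement in device users, and the protocol never mentions non-inferiority. That lean stands, but it does not close the gap. Section 7 states a null and an alternative outright. If it is only sizing, the test actually planned has neither a stated hypothesis nor a power. The protocol's commitment to compare scores does not settle the framework.

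A reader might point to the secondary analyses mentioned in SAP 12. They serve secondary hypotheses, none is defined, and section 7 is not presented as secondary.

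A reader might also infer that the team could choose freely between parametric and nonparametric results once data are seen. That goes too far, because SAP 12 names ANOVA as primary and gives non-normality as the trigger. The defects are narrower: an unnamed method, no normality criterion, and the optional wording of 11.1 against the definite wording of 12.

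Finally, the power shortfall is a sample-size defect in its own right. It matters here only because it shows that section 7's power cannot simply be carried over.

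**Conclusion.** The mismatch is certain from the text and needs no arithmetic: the stated hypothesis gets no verdict, and the stated 90% power does not belong to the planned test. If the stated hypothesis were tested, power at 50 per arm would be about 17% or 26%, assuming absolute points, equal true rates of 50% and no losses. A relative margin or any loss of subjects lowers it.

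It would be tempting to conclude that the planned ANOVA is itself underpowered. The documents do not support that, because they give neither an SD nor a target difference. All that can be stated is the detectable effect in SD units. It would also be tempting to quote power at the 32 per group in Protocol 9.4. Protocol 11.4 says no interim analysis is planned, so figures at full alpha for 32 would presuppose a look that the documents have not reconciled.

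This must be fixed before the primary result is interpreted. The sponsor has to choose the framework.

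**What to change.** Make hypothesis, endpoint and test agree before outcome data are reviewed by arm. If that has already happened, disclose it and date the change in SAP 2, and also in SAP 13 if it departs from the protocol.

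- **Route A, superiority on Mankoski change after 2 weeks.** Replace the section 7 hypotheses. Delete the two-proportion basis and its 90% power, and insert the detectable differences in step 4 by evaluable number. Name as the primary test the baseline-adjusted device-minus-SOC contrast at the end of the 2-week treatment period, with its confidence interval. Name one nonparametric method with a fixed role, either sensitivity or a fallback with a stated criterion, and word 11.1 and 12 alike.
- **Route B1, non-inferiority on proportions.** Define the responder from Mankoski change. Compare the lower confidence limit for device minus SOC with −10 points at a stated level and sidedness. Restate power as about 17% or 26% at 50 evaluable per arm (16% or 24% at 45; 14% or 23% at 40). The normality and nonparametric text does not apply to this endpoint.
- **Route B2, non-inferiority on the mean.** Set and justify a margin on Mankoski change, test the confidence limit against it, and state power for that margin. Name the contrast and the nonparametric role as in Route A.

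In every route:

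- Name which of ITT and PP is primary, and which of complete case and carry-forward applies.
- Say what the 2 weeks are counted from. Protocol 9.2 starts assessment immediately, 15.2 delivers the device in 3 to 5 days, and 9.4 counts 14 consecutive days of use.
- State that a non-significant difference will not be read as non-inferiority.
- Keep figures for 32 per group out of section 7 until Protocol 9.4 and 11.4 are reconciled.
- Minor: in SAP 11.1, name SOC as the comparator in place of sham.

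**Cost.** Rewording of the SAP sections concerned and routine programming, with no new data. Route A gives up a non-inferiority claim that 50 per arm supports poorly at the SAP's own inputs, and leaves power in SD units. Route B1 means stating low power openly. Route B2 needs a margin justification that the documents do not contain.

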12.1. Primary Endpoints

The primary endpoints of this study will be to compare the reduction of pain symptoms from baseline on the Mankoski Pain Scale after 2 weeks of treatment with the OrthoCor Active System device and Standard of Care.

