12.4. Handling Missing Data

Only participants with complete available data will be used in the statistical analysis, i.e., a complete case analysis. For missing visits, an imputation of last visit carried forward will be considered.

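### Fifty per arm does not follow from the SAP's sizing inputs: with a 10-point absolute margin they need 429 or 526 per arm, and 50 gives that test 26% or 17% power, not 90%

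*SAP*

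**What the plan says.** SAP section 7 (Sample Size) treats the outcome as binary, improved or not, and frames the trial as non-inferiority: "The alternative hypothesis is that the experimental treatment is non-inferior to the standard of care". It says the size per group rests on a comparison of two proportions with 50% response on the device, "assuming a 50% response for SOC and a non-inferiority margin of 10% assuming 90% power". On error control it adds: "The assumed confidence is 95% or a type 1 error rate of 5" per cent. The next paragraph gives the enrolment: "The study will enroll 100 subjects, up to 50 using the OrthoCor Active System", with up to 50 on standard of care (SOC).

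The section shows no formula and no computed number. It does not say whether the 10% margin is absolute or relative, or whether the 5% is one- or two-sided. The protocol (synopsis and section 8.3) gives the same ceiling of 50 per arm without a justification.

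The analysis sections describe a different test. SAP section 12.1 sets the primary endpoint as a plan to "compare the reduction of pain symptoms from baseline on the Mankoski Pain Scale after 2 weeks of treatment" between the arms. Section 12 says the "primary analysis will consist of ANOVAs for repeated measures". Section 11.1 adds: "All hypotheses are performed at an alpha equal to 0.05". Section 12 contains no responder definition, margin or confidence-limit rule.

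**The concern.** Section 7 offers one basis for the group size, a 90%-power calculation, and then gives 50 per arm. A reader will take it that 50 per arm delivers 90% power. A 10-point margin around a 50% response rate is demanding, because binomial variance is greatest there, and sizes in the hundreds per arm would be expected.

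Two things are at stake. If the trial is meant to show non-inferiority on a binary response, it would probably miss that aim even when the two treatments are equally good. If it is meant to test a difference in Mankoski change, the only power statement in the SAP belongs to another test, and a reader cannot tell what 50 per arm can show on the primary endpoint. A non-significant ANOVA could also be misread as support for the section 7 non-inferiority hypothesis, although the analysis plan contains no test of it.

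**Working it through.** **Inputs (SAP section 7).** SOC response 0.50; device response 0.50, so the true difference is 0; margin 10%; power 90%; type 1 error 5%; planned size up to 50 per arm, 1:1. The margin scale and the sidedness are not stated, so each is taken both ways: 10 points (absolute) or 10% of 50% = 5 points (relative); one-sided 5%, or one-sided 2.5% (the lower limit of a two-sided 95% interval). No dropout allowance is stated and none is applied.

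**Can 50 be reproduced?** The unpooled normal approximation is

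n per arm = (z_α + z_β)² × [0.5×0.5 + 0.5×0.5] / margin²

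with z_β = 1.282, and z_α = 1.645 or 1.960. The squared sum is 8.564 or 10.507.

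| Margin | One-sided 5% | One-sided 2.5% |
|---|---|---|
| 10 points | 8.564 × 0.5 / 0.01 = 428.2 → **429** | 10.507 × 0.5 / 0.01 = 525.4 → **526** |
| 5 points | 8.564 × 0.5 / 0.0025 = 1,712.8 → **1,713** | 10.507 × 0.5 / 0.0025 = 2,101.5 → **2,102** |

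For the 10-point margin this is 429/50 = 8.6 or 526/50 = 10.5 times the planned size.

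Other formulas do not recover 50 either:
- 80% power: 310 or 393 per arm.
- Variance restricted under the null (Farrington–Manning): about 426 or 523.
- Superiority formula for a 10-point difference at 90% power, one- or two-sided, with or without continuity correction: 423 to 538.
- Single-sample formula: 215 or 263.

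Only a changed input gives about 50. At equal 50% rates, 50 per arm reaches 90% power with a margin of about 29 points (one-sided 5%) or 32 points (one-sided 2.5%). With the 10-point margin kept, a true device response of about 70% needs 44 or 54 per arm, but the SAP states 50%.

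**Power of the binary test at 50 per arm.** The standard error is √(0.5/50) = 0.10, and power = Φ(margin/0.10 − z_α).

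| Margin | One-sided 5% | One-sided 2.5% |
|---|---|---|
| 10 points | Φ(1 − 1.645) = 26.0% | Φ(1 − 1.960) = 16.9% |
| 5 points | Φ(0.5 − 1.645) = 12.6% | Φ(0.5 − 1.960) = 7.2% |

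Exact binomial enumeration of the Wald test with the 10-point margin gives 24.3% and 18.4%. By the normal approximation, the chance of failing to show non-inferiority when the arms are truly equal is 74.0% or 83.1%.

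**What the size can detect on the Mankoski scale.** The documents give no SD, so this can be expressed only in SD units. The figures below are for a two-sample t-test, two-sided 5%, as an approximation to the planned ANOVA. The rows for 45 and 40 assume that 10% or 20% of subjects drop out of the analysis; section 12.4 says "Only participants with complete available data will be used in the statistical analysis".

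| Analysed per arm | 80% power | 90% power |
|---|---|---|
| 50 | 0.57 SD | 0.65 SD |
| 45 | 0.60 SD | 0.69 SD |
| 40 | 0.63 SD | 0.73 SD |

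**The case against.** The strongest reply is that the SAP never says in words that 50 per arm gives 90% power. The inputs and the enrolment stand in separate paragraphs, and 50 is a ceiling that may reflect feasibility. It is true that the link is implied. But section 7 says the size is based on these inputs and offers no other basis. If 50 is a feasibility cap the SAP should say so, and the 90% figure would still not apply to it.

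A second reply is that the primary analysis is an ANOVA, so the binary power is beside the point. It stands to this extent: the 26% and 17% say nothing about the ANOVA. That leaves the primary endpoint with no power statement at all.

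Third, the SD-unit figures are rough. A single-time-point t-test may misstate the sensitivity of an analysis that uses daily scores, the SD meant has to be defined, and nonparametric methods are allowed. The 10% and 20% losses are assumptions: section 12.4 also says carrying the last visit forward will be considered, and section 12.6 puts all subjects in the ITT analysis. These limits are accepted. The figures describe sensitivity and are not needed for the main finding.

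Finally, protocol section 9.4 allows the study to be considered complete after 32 per group. That is a separate issue, but at 32 per arm the binary test (10-point margin) would have only about 20% or 12% power.

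**Conclusion.** The planned size is inconsistent with the stated inputs under every reading of them. With a 10-point absolute margin, 90% power needs 429 per arm (one-sided 5%) or 526 (one-sided 2.5%), and 50 per arm gives 26% or 17%. With a relative margin the need is 1,713 or 2,102, and the power 13% or 7%. The gap is too large to come from the choice of formula, sidedness or rounding.

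These figures assume true response rates of 50% in both arms, as section 7 does, and all 50 per arm analysed; any loss lowers power further. They apply only to the binary non-inferiority test. The power of the planned Mankoski analysis cannot be worked out from the documents. This must be corrected, because the only power claim in the SAP fits neither the planned size nor the planned analysis.

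**What to change.** No extra enrolment is needed.

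1. In SAP section 7, withdraw 90% power as a basis for 50 per arm. State the power that 50 per arm gives the binary comparison, naming the sidedness and margin scale: about 26% (one-sided 5%) or 17% (one-sided 2.5%) if the sponsor confirms 10 absolute points, or 13% or 7% if the margin was meant as relative. If 50 was chosen for feasibility, say so.
2. Reconcile the section 7 hypotheses with sections 11 and 12. Either replace them with a difference hypothesis on Mankoski change, or keep non-inferiority and add to section 12 a responder definition, the margin and a confidence-limit rule. Date the decision, give its rationale, and record that it was made without reference to results: the trial is open label and the SAP history runs to November 2023.
3. If the difference hypothesis is adopted, report the sensitivity of 50 per arm: about 0.57 SD at 80% power or 0.65 SD at 90% (two-sided 5%, two-sample approximation, all 50 analysed), weakening to about 0.63 or 0.73 SD if 40 remain. Define which SD is meant. Present this as what the size can detect, not as its justification, since no Mankoski SD is given.

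The cost is a rewrite of section 7, one sponsor decision on the hypothesis, and an addition to section 12 if non-inferiority is kept. Visits and data collection do not change. The downside is a less favourable power statement.
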